#### 6.4 Primary variable

There are two primary variables:

1. LCIG monotherapy 1 (yes, no) at LCIG initiation and at 3, 6, 9, and 12 months after LCIG initiation

with the following definition:

- LCIG monotherapy means that the patient is not on any add-on PD medication or PD therapy at the respective time point.
- 2. LCIG monotherapy 2 (yes, no) at LCIG initiation and at 3, 6, 9, and 12 months after LCIG initiation

with the following definition:

LCIG monotherapy means that the patient is allowed to take an add-on PD medication or PD therapy at the respective time point, however, only in the evening after the LCIG infusion is completed (i.e. reason for start of add-on PD medication: other).

Additional specifications for both variables are:

- Medications for indications secondary to PD are allowed.
- If the reason for add-on PD medication is missing the medication will be considered as taken during LCIG infusion (i.e. no monotherapy).
- LCIG initiation date is the start date of the first LCIG infusion.
- 3 months after LCIG initiation is calculated as LCIG initiation date + rounded (3 [months] x 30.4 [days]). 6, 9, and 12 months after LCIG initiation will be calculated analogously.
- For LCIG initiation date with missing day the 15th will be used.

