#### Reasons:

- For each add-on PD medication/therapy at the time points LCIG initiation and at 3, 6, 9, and 12 months after LCIG initiation and at visit::
  - Reason for start (multiple answers)
  - If not ongoing: reason for discontinuation (multiple answers)
- Reason for change on LCIG dose in general
- Reason for LCIG dose changes (multiple answers) by 5%, 10%, 15%, 20% or 25% or higher
- Reason for substantial LCIG dose changes (multiple answers) with substantial change defined as any increase or decrease of the total daily LCIG dose by more than 20%
- Latency and duration of treatments:
  - For patients with add-on PD medication or PD therapy at LCIG initiation: Time from LCIG initiation until LCIG is given as a monotherapy (separately for monotherapy 1 and monotherapy 2 definition)

[figure not shown]
Only patients with add-on PD medication or PD therapy at LCIG initiation

 For patients with add-on PD medication or PD therapy at LCIG initiation and separately for patients with and without ongoing monotherapy at visit: Duration of LCIG monotherapy (separately for monotherapy 1 and monotherapy 2 definition) Only patients with add-on PD medication or PD therapy at LCIG initiation Analysis a) Without ongoing monotherapy until visit

Analysis b) With ongoing monotherapy until visit

- For each add-on PD medication/therapy:
   Time from LCIG initiation until the respective add-on PD medication/therapy is started or changed
- Time from LCIG initiation until the first LCIG dose change by 5%, 10%, 15%, 20% or 25%
- Time from LCIG initiation until the first substantial LCIG dose change with substantial change defined as any increase or decrease of the total daily LCIG dose by more than 20% in relation to first LCIG infusion
- LCIG monotherapy (1 and 2) vs. LCIG plus add-on PD medication:
  - o HCRU:
    - Primary occupation (retired, on sick leave, unemployed, working full time, working part-time, student)
      - If retired: due to PD (yes, no)
      - If on sick leave: due to PD (yes, no)
      - If unemployed: due to PD (yes, no)
    - Permanent living in a nursing home/institution (yes, no)
    - Help in daily activities
    - Frequency of visits:
      - General practitioner

- Nurse
- Occupational/speech therapist
- Physiotherapist
- Psychologist and/or psychiatrist
- Dietician
- Discussion of LCIG monotherapy (yes, no, patient did not remember)
- Offering of LCIG monotherapy (yes, no, patient did not remember)

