## 7 Statistical methodology

## 7.1 General methodology

All statistical analyses will be carried out by means of the SAS® package (version 9.4).

Quantitative data (e.g. age) will be described by the statistical parameters valid N, missing N, mean, standard deviation (SD), minimum, the 25%-quartile, median, the 75%-quartile, and the maximum.

Qualitative data (e.g. gender) will be presented by means of (absolute and relative) frequency distributions. If applicable, two methods will be followed for calculation of percentages. The first method considers missing data as a separate group, which results in the same sample size for all parameters. The second method of calculation is based on the valid data per parameter, excluding patients with missing values ("valid data analysis"). Accordingly, this results in different sample sizes. In general, description of results within the report refers to the "valid data analysis".

For categorical variables associated with score values, the mean will be calculated as well.

Two-sided 95% confidence intervals will be provided for the primary, and if applicable, the secondary variables defined by proportions.

Statistical methods which differ from the above mentioned methods or require further description will be addressed in the following sections.

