#### 7.6 Secondary variables

The secondary variables will be evaluated for FAS.

Secondary variables will be analyzed overall and separately for the following three groups:

- Patients on monotherapy 1 at 12 months after LCIG infusion (see Section 6.4)
- Patients on monotherapy 2 at 12 months after LCIG infusion (see Section 6.4)
- Patients not on monotherapy 2 at 12 months after LCIG infusion (see Section 6.4)

Regarding 'Add-on PD medication' patient based means that a therapy type will only be counted once per patient. The variables total daily dose, LEDD and posology will additionally be analyzed per category by summing up the values of the corresponding medication/therapy.

Regarding total dose per day the difference will be calculated between the time points LCIG initiation start, 12 months after LCIG initiation start and visit as follows:

- Total dose per day at 12 months after LCIG initiation start minus total dose per day at LCIG initiation start
- Total dose per day at visit minus total dose per day at LCIG initiation start
- Total dose per day at visit minus at 12 months after LCIG initiation start

If applicable, levodopa equivalent daily dose (LEDD) will be calculated separately for each medication/therapy as total daily dose in mg multiplied with the respective factor (from Table 7-1; [1], [2], [3]). Exceptions are entacapone, tolcapone and opicapone: irrespective of the entacapone dose (or tolcapone or opicapone dose, respectively) the corresponding levodopa dose is multiplied by the given factor. This will then be considered as LEDD for entacapone (or tolcapone or opicapone, respectively).

The total daily LEDD will be the sum over all daily LEDDs which were calculated separately for each medication at the respective time point.

Table 7-1: Factor for levodopa equivalent daily dose

Medication	Factor
Levodopa/carbidopa	1.11
Levodopa/benserazide	1
Levodopa/carbidopa/entacapone	1.33
Amantadine	1
Apomorphine	10
Cabergoline	80
Entacapone	concomitant levodopa multiplied by 0.33
Tolcapone	concomitant levodopa multiplied by 0.5
Pramipexole	100
Rasagiline	100
Ropinirole	20
Rotigotine	30
Selegiline oral	10
Opicapone	concomitant levodopa multiplied by 0.65
Safinamide	
Budipine	5

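### SAP 6.5 leaves patients who start on LCIG monotherapy out of the duration analysis and never combines ended with ongoing spells, so the average duration of monotherapy is not estimated; handling of latency needs confirming

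*SAP*

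**What the plan says.** Protocol 8.0 and SAP 3.2 set as a secondary objective the description of latency to monotherapy and of its average duration. Protocol 9.1 lists both times as endpoints. None of these sections limits the patients.

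SAP 6.5 (Latency and duration of treatments) defines latency, in patients with an add-on at initiation, as "Time from LCIG initiation until LCIG is given as a monotherapy (separately for monotherapy 1 and monotherapy 2 definition"). The duration item is restricted to those having "add-on PD medication or PD therapy at LCIG initiation and separately for patients with and without ongoing monotherapy at visit: Duration of LCIG monotherapy". The two tables are "Analysis a) Without ongoing monotherapy until visit" and "Analysis b) With ongoing monotherapy until visit".

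On method, SAP 7.6 states that "The secondary variables will be evaluated for FAS" and adds groups by monotherapy status at 12 months. SAP 7.1 says that quantitative data "will be described by the statistical parameters valid N, missing N, mean, standard deviation (SD), minimum", quartiles and maximum. Neither section gives a time-to-event method. SAP 6.7 on missing data covers rating-scale items only.

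SAP 6.4 has two definitions. Monotherapy 1 allows no add-on. Monotherapy 2 allows one, "however, only in the evening after the LCIG infusion is completed". The starting point is fixed: "LCIG initiation date is the start date of the first LCIG infusion".

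**The concern.** Restricting to patients with an add-on at initiation makes sense for latency, since the others have a latency of zero. For duration it removes people who have a monotherapy spell. Under definition 1, everyone on monotherapy from the first infusion is lost. Under definition 2 the rule is also inconsistent: a patient with an evening-only add-on at initiation is kept and a patient with no add-on is dropped, although both meet the definition on that day.

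The split raises a separate problem. A spell that has ended by the visit had to be short enough to end, and an ongoing spell is elapsed time so far. Follow-up is at least 12 months with no stated maximum, so both summaries depend on when the visit happened. Readers would get two figures, neither of which is the named quantity.

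**Working it through.** **1. The plan's own figures.** No figure is stated for latency or duration. The only computed design figure concerns the primary percentages: 1.96² × 0.5 × 0.5 / 0.05² = 384.15, rounded up to 385. It reproduces, and this point does not touch it.

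**2. Does any planned analysis pool the spells?** SAP 7.6 asks for results overall, but there the word contrasts with the groups by 12-month status. It applies to variables that 6.5 has already restricted and split. Averaging a) and b) together would still count unfinished spells as finished. SAP 2.5 promises that substantial deviations from the protocol analysis are described; none is described here.

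**3. What a) and b) measure.** Let a spell start W years before the visit and last D, exponential with mean m. Then:

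- a) = E[D | D ≤ W] = [m(1 − e^(−W/m)) − W e^(−W/m)] / (1 − e^(−W/m))
- b) = E[W | D > W], which for fixed W is W whatever m is

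With W = 2 and m = 2: a) = (1.264 − 0.736)/0.632 = 0.84 y, or 42% of the mean; b) = 2 y. With W = 2 and m = 5: a) = (1.648 − 1.341)/0.330 = 0.93 y, or 19%; b) is still 2 y, or 40%.

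Averaging numerator and denominator over W gives the grid below. Assumptions: exponential latency with median 0.75 y; visit uniform from 1 y (the inclusion minimum) to 3, 6 or 10 y (Protocol 7.0 puts LCIG on the market for over 10 years); no LCIG discontinuation. Entries are a) / b) as a fraction of the true mean.

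| True mean (y) | Visit 1–3 y | Visit 1–6 y | Visit 1–10 y |
|---|---|---|---|
| 0.5 | 0.78 / 1.20 | 0.91 / 1.29 | 0.95 / 1.30 |
| 1 | 0.56 / 0.91 | 0.78 / 1.17 | 0.88 / 1.23 |
| 2 | 0.35 / 0.56 | 0.57 / 0.89 | 0.74 / 1.08 |
| 5 | 0.16 / 0.25 | 0.30 / 0.46 | 0.45 / 0.69 |
| 10 | 0.08 / 0.13 | 0.16 / 0.25 | 0.26 / 0.40 |

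a) is always too low. b) is above the mean in 6 of 15 cells and below it in 9, so its direction cannot be predicted. The true median (0.693 × mean) lies beyond the longest follow-up in 3 of the 15.

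**4. The excluded group (definition 1).** Its size is unknown. Shares borrowed from Protocol 7.0, none measured at LCIG initiation in routine care, give:

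- 400 × (1 − 0.89) = 44
- 400 × (1 − 0.80) = 80
- 400 × (1 − 0.37) = 252
- 400 × (1 − 0.969) = 12 at most, if everyone on oral levodopa before LCIG in the cited Italian study was still on it at the first infusion

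Let f be the share on monotherapy from initiation, with all others reaching it, and r their mean duration relative to the others. The restricted mean over the full mean is 1/(1 + f(r − 1)). With r = 1 it is 1.00. With r = 2 it is 0.97 (f = 0.031), 0.90 (0.11), 0.83 (0.20) and 0.61 (0.63). With r = 0.5 it is 1.02 to 1.46.

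**5. Limits of the remedy.** Only patients still on LCIG are enrolled (Protocol 9.2.1, 9.9). Take a true mean of 2 y: median 1.39 y, 24-month restricted mean 2(1 − e^(−1)) = 1.26 y. If LCIG discontinuation is equal on and off monotherapy (5% or 10% a year), the Kaplan-Meier median is 1.38–1.39 y. With rates on/off of 5/15, 5/30 or 15/5% a year (18 scenarios), it runs from 1.19 to 2.01 y. The restricted mean is then about 0.93 to 1.15 of its own truth. Against the 2 y mean it is about 0.59 to 0.73, which is why it must not be called the unrestricted average.

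**6. Latency.** Suppose patients who do not reach monotherapy fall into missing N. With median latency 0.25, 0.75 or 1.5 y among those who ever reach it, 60%, 80% or 100% reaching, and the same visit windows, the reported median is 0.26 to 1.00 of the at-risk median in the 26 of 27 scenarios where the latter is reached. If all eventually reach it, the ratio is 0.50 to 1.00. The lowest values therefore come largely from assuming that 20% to 40% never do.

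**The case against.** The study is descriptive, and SAP 7.10 calls it exploratory and open to extensions. The a)/b) split openly separates finished from unfinished spells. Duration could be read as what follows the latency period, which would explain the restriction. Patients on monotherapy from the first infusion do appear in the percentages at every time point, including times after 12 months (SAP 7.5). All of this is true and limits the harm. It does not supply an average duration: a descriptive plan must still describe the quantity it names, and here a written rule removes relevant patients.

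Three stronger readings are tempting but not supported.

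- A reader might infer that the SAP has no rule for patients who never reach monotherapy. A figure directly after the latency item is not shown and could define it, so only the silence of the visible text can be claimed. A time summarised among those who reached monotherapy is also legitimate if labelled so.
- A reader might infer that most patients are excluded from duration. The borrowed shares run from 12 to 252 of 400. Protocol 7.0 also says that other therapies are usually tapered during titration, and a patient tapered after the first infusion is still included.
- A reader might infer that the primary result is affected. It uses the whole full analysis set and is not.

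**Conclusion.** The duration part holds on the text alone. The SAP restricts an unrestricted objective without giving a reason, is inconsistent for definition 2, and plans two summaries that are not an average duration. The size of the effect in this study is not known. The ratios above illustrate it under assumed exponential times, visit windows and, for selection, discontinuation rates. The extremes of 8% and 13% need a 10-year mean with at most 3 years of follow-up. Leaving out patients who start on monotherapy does no harm if their spells last as long as the others'. The split of ended from ongoing spells matters whatever the size of that group. For latency this is a reporting point to confirm. The change is worth making before database closure because the objective is named and the correction is cheap.

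**What to change.** 1. **Duration.** For each definition, use Kaplan-Meier in all patients of the full analysis set ever on monotherapy, including from initiation. Time runs from the first day of monotherapy to the first day the definition is no longer met, for the first continuous spell, censored at the visit. Report the median, quartiles, 95% confidence interval and the share of spells lasting at least 12 months (the long-term cut in Protocol 9.2.7.7). Add a restricted mean to a time fixed before database closure, labelled as a mean over that period. Keep a) and b) as supportive tables.
2. **Incomplete add-on dates.** Use one rule consistent with the tapering text of SAP 6.5: no imputation, with the number left out reported. Otherwise justify a different rule and show a sensitivity analysis.
3. **Latency.** Keep patients with an add-on at initiation (for definition 2, those not already meeting it). Report how many had not reached monotherapy by the visit and how many were on it from initiation. Give a time-to-event estimate censored at the visit, beside or in place of the summary among those who reached it.
4. **Scope.** State that all these estimates are conditional on still being on LCIG at the visit.

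The cost is SAP wording, a standard SAS survival procedure and some programming. No new data are needed, because add-on start and stop dates are already collected (Protocol 9.2.7.5) and the SAP already uses the visit date. The downside is that some medians may not be reached, and selection on remaining on LCIG stays and can bias the Kaplan-Meier estimates either way.

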To assess the generalizability of the data from the patients enrolled, the physician will be asked to document on a separate Case Reporting Form the number of patients who are eligible but refuse to participate in the study. Only age ranges (<30 years, 30-45 years, 45-65 and > 65 years) and reason(s) for not participating will be collected.

The primary endpoint of this PMOS will be the percentages of APD patients on LCIG monotherapy right after LCIG initiation and at 3, 6, 9, and 12, respectively.

The secondary endpoints are:

- Descriptive data from patient's PD medication:
 - For add-on PD medication: percentage of patient on each PD medication (by drugs and class), total daily dose and levodopa equivalent Daily dose (LEDD), posology (number of times per day);
 - For LCIG infusion settings and substantial dose adjustments: total dose per day and specific for each type of dose (morning dose and continuous dose) and number of hours of infusion.

- Tapering process: number of days required for the tapering process, total dose per day and posology for add-on PD medication prior to LCIG initiation, at LCIG initiation (titration) or during ongoing LCIG treatment
- Main reasons for introduction or tapering of add-on PD medication or LCIG substantial dose adjustments
- Latency and duration of treatments data:
 - Number of days or months from LCIG initiation until LCIG is given as a monotherapy and the duration of LCIG monotherapy.
 - Number of days or months from LCIG initiation until the introduction or tapering of each PD medication, or until any LCIG substantial dose adjustments.
- LCIG monotherapy vs LCIG plus add-on PD medication data:
 - Healthcare Resource Utilization, as measured by Healthcare Resource Utilization Questionnaire (HCRU)
 - Patient's, caregiver's, and physician's overall preference on LCIG monotherapy vs. LCIG plus add-on PD medication, percentage of patient's and physician's preference for each of the options
 - Predictors for LCIG as monotherapy vs. LCIG plus add-on PD medication based on the patient's profile, including socio-demographics, clinical status (motor and non-motor symptoms), Levodopa-equivalent dose (LED), PD medication and Quality of Life
 - Predictors for LCIG as monotherapy vs. LCIG plus add-on PD medications based on the physician's profile including experience as measured by number of years on APD patient management, number of years using LCIG therapy, and number of patients on LCIG therapy

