9.2.7.5 Previous PD medication and add-on PD treatment during **LCIG Treatment**

Data on previous PD medication (right before initiation of LCIG treatment) will include date of drug initiation and/discontinuation, reason for its discontinuation, drug name, total dose per day, posology, and attempts of previous device-aided therapies (e.g., CSAI, DBS).

Data on add-on PD medication upon LCIG initiation or during LCIG treatment will include date of drug initiation/discontinuation, drug name, total dose per day, posology, tapering* process (duration and posology), starting and end date of LCIG titration, reasons for add-on drug therapy (severity and frequency), timing of add-on drug (during/outside of infusion hours).

Levodopa equivalent daily dose (LEDD) table published by Tomlinson, et al will be used to calculate LEDD. [47]. Each PD medication amount should be multiplied by the appropriate value to obtain the corresponding LEDD. Adding together the corresponding LEDD for each PD medication, will be providing the total LEDD.

9.2.7.6 **Concomitant Disease and Medication**

Information on concomitant disease and medication (non-PD treatment) will be collected and reported in the eCRF, including drug name, indication, start/stop date, and dosages.

^{*}The term "tapering" is used within this study in the context of drug treatment. It refers to the process of reducing a certain drug dosage incrementally (over a few days or weeks), instead of its abrupt discontinuation. For some PD medications a tapering process is needed to avoid a withdrawal syndrome

9.2.7.7 **LCIG Treatment**

Information on LCIG treatment from initiation until the day of the visit will be documented in the eCRF, including reason(s) for initiation of LCIG treatment, date of introduction of LCIG, use of nasojejunal tube, date of PEG-J procedure, date of titration and duration of titration process, infusion settings (infusion time, morning dose, continuous infusion rate, total daily dose) and dose modification (number of dosage changes, new infusion settings or temporary interruptions in LCIG daily infusion rate and reasons for dosage adjustment).

A LCIG substantial dose adjustment is defined as any increase or decrease of the total daily LCIG dose by more than 20% of total daily dose.

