## 3.2 Secondary objectives

The secondary objectives of this study are:

- To describe PD medication management, and the main reasons justifying their use, directly prior to LCIG initiation, at LCIG initiation and during long-term LCIG treatment
- To describe LCIG infusion settings and substantial dose adjustments and the respective reasons
- To describe the Healthcare Resource Utilization (HCRU)
- To identify the physician's and patient's/caregiver's overall preference for the pharmacological treatment approach using LCIG as monotherapy vs. LCIG plus add-on PD medication
- To identify predictors for achieving long-term monotherapy with LCIG vs. LCIG plus add-on PD medication, based on the patient's profile and the physician's profile
- To describe the latency from LCIG initiation until LCIG is given as a monotherapy and the average duration of LCIG monotherapy
- To describe the latency from the initiation of LCIG therapy until the introduction or tapering of each PD medication, or until substantial dose adjustments of LCIG
- To evaluate the percentage of patients who are on LCIG monotherapy, PD medication management and HCRU for the participating countries who have enrolled a minimum of 20 study subjects

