#### Tapering process:

- o For each add-on PD medication/therapy over all treatment phases:
  - Minimum total daily dose; if the add-on PD medication is stopped, the minimum total daily dose will be set to 0
  - Maximum total daily dose
  - The tapering process is any change in the dose concentration (decreasing or increasing dose) and the number of days for tapering process is the number of days between maximum and minimum daily dose; patients with minimum (or maximum, respectively) daily dose not at the end of the tapering process will be checked. A maximum duration of ca. 2 months of the tapering process is allowed (otherwise the tapering process is set to missing). Dates which are incomplete will not be imputed and, thus, no tapering process can be identified (missing). If the add-on PD medication is stopped, but no entry with

[figure not shown]
dose = 0 is recorded the stop date will be used as date of minimum total daily dose.

- For each add-on PD medication/therapy:
   Only for the time period of tapering process:
   If within the tapering process: at the time points LCIG initiation and at 3, 6, 9, and 12 months after LCIG initiation and at visit:
  - Total daily dose (except all 'Other', Anticholinergics, and Surgical therapy; Apomorphine only if possible)
  - Posology (i.e. number of intakes per day; except all 'Other' and Surgical therapy)

[figure not shown]

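### SAP 6.5 times each add-on to a start or any change, so a dose increase can end the latency that the protocol ties to tapering

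*SAP*

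**What the plan says.** The SAP repeats the protocol's secondary objective in section 3.2: "To describe the latency from the initiation of LCIG therapy until the introduction or tapering of each PD medication". The matching protocol endpoint (9.1, also in the abstract) is "Number of days or months from LCIG initiation until the introduction or tapering of each PD medication". The note to protocol 9.2.7.5 fixes the meaning of tapering: "It refers to the process of reducing a certain drug dosage incrementally (over a few days or weeks), instead of its abrupt discontinuation".

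SAP 6.5, under latency and duration of treatments, has one line for this endpoint, for each add-on: "Time from LCIG initiation until the respective add-on PD medication/therapy is started or changed". Elsewhere in SAP 6.5, under the tapering process, the SAP gives its own meaning: "The tapering process is any change in the dose concentration (decreasing or increasing dose".

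SAP 7.6 adds no method for latencies. It says "Secondary variables will be analyzed overall and separately for the following three groups", and the groups are defined by monotherapy status at 12 months. None is defined by whether the patient was on the drug at LCIG initiation, or by whether the event was a start, a reduction or an increase.

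**The concern.** Introduction and tapering are opposite decisions, usually made in different patients and at different times. Protocol 7.0 describes other oral or transdermal drugs as usually being tapered during titration, with combination therapy needed later in some patients. The objective is to show when physicians do each.

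The SAP line raises two problems. First, it replaces reduction by change of any direction, so a patient whose dose was raised counts as having reached the event. Second, if it is programmed as one variable, patients newly given a drug are summarised together with patients whose existing drug was altered. The result then reflects how many patients of each kind there are as well as how long each step took, and readers could take it for a tapering time or an introduction time when it is a mixture. The line also leaves open whether the first change is meant, whether a stop counts as a change, and what happens to patients without an event.

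**Working it through.** **Definitions side by side**

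- Event in the protocol: introduction, or tapering in the sense of "It refers to the process of reducing a certain drug dosage incrementally".
- Event in the SAP: start, or change without direction. The SAP's tapering text expressly admits increases, so nothing in SAP 6.5 excludes them.
- Patients at risk: not restricted in the add-on line. By contrast, the monotherapy latency in the same list is limited to patients with add-on treatment at LCIG initiation, and its split is spelled out: "Time from LCIG initiation until LCIG is given as a monotherapy (separately for monotherapy 1 and monotherapy 2 definition".
- Stops: the SAP's tapering text sets the minimum dose to zero when a drug is stopped, while the protocol sets tapering apart from abrupt discontinuation.
- Other add-on variables in SAP 6.5: use, dose and LEDD at fixed time points, duration of the tapering process, and reasons. None is a time from LCIG initiation to a start or to a first reduction.

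**Plan's own figure**

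The documents give no figure for this endpoint. The only size calculation, in protocol 9.5, concerns the primary percentages: 1.95996² × 0.5 × 0.5 / 0.05² = 384.15, rounded up to 385. It reproduces and is not affected.

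**Illustration (all inputs assumed, none from the documents)**

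Times are exponential and independent, with no censoring. A share q of patients is on the drug at LCIG initiation. Among them, the median time to first reduction is R = 0.5 or 2 months and to first increase I = 12 months. In the others, the median time to first start is S = 12 months.

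1. Share of users whose first change is an increase = (1/I) / (1/I + 1/R). For R = 0.5: 0.0833/2.0833 = 4%. For R = 2: 0.0833/0.5833 = 14%.
2. Median time to first change in users = 1 / (1/I + 1/R). For R = 0.5: 0.48 months. For R = 2: 1.71 months. If reductions were as slow as increases (R = 12), half of first changes would be increases and the median would be 6 months instead of 12.
3. The pooled median t solves q × 2^(−t(1/R + 1/I)) + (1 − q) × 2^(−t/S) = 0.5. Check at q = 50%, R = 2, t = 3.93: 0.102 + 0.398 = 0.500.

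| Share on drug at initiation | Pooled median, R = 0.5 | Pooled median, R = 2 |
|---|---|---|
| 20% | 8.1 months | 8.4 months |
| 50% | 1.7 months | 3.9 months |
| 80% | 0.7 months | 2.2 months |

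Within each column the time to introduction (12 months) and the time to reduction are constant; only the mix changes. The mix will differ between drugs: protocol 7.0 cites an Italian observational study with 96.9% on oral levodopa and 64.1% on dopamine agonists before LCIG.

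**The case against.** The strongest reply is that pooling is inferred from the word *or*. The protocol endpoint already joins introduction and tapering that way, so the SAP inherits part of the ambiguity. The next SAP line, on LCIG dose changes, lists several percentage thresholds joined by *or*, and these can only be separate outputs. The add-on line could therefore mean two times. That stands: on this reading, time to start gives time to introduction. It does not rescue tapering, because *changed* would still include increases.

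A reader might go further and infer that neither latency can come out of this study. The documents do not support that. Protocol 9.2.7.5 collects start and stop dates, doses and taper details for each add-on, so both can be derived. A reader might also infer that drugs carried over from before LCIG would get negative times or be handled wrongly. No rule for them is stated, so this is a gap and not a documented error.

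Two further points limit the harm. SAP 7.1 reports quartiles as well as the median, so a strongly two-peaked distribution might show. SAP 6.5 also tabulates use of each add-on at LCIG initiation, at 3, 6, 9 and 12 months and at the visit, which gives a coarse picture of timing, though not a latency.

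Finally, SAP 7.10 allows changes if the data suggest them. But SAP 2.5 makes the written methods binding for programming and says that substantial departures from the protocol are described. This one is not.

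**Conclusion.** The mismatch is real. Read literally, the SAP lets a dose increase end the tapering latency, contrary to the protocol's definition, and this holds on either reading of the line. Pooling of starts with changes holds only on the one-variable reading, which is the more natural one but not the only one.

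The size cannot be taken from the documents. Under the assumptions above, mixing directions alone shortens the tapering median only slightly when reductions come early (2 to 1.7 months), and more where reductions are no faster than increases. Pooling matters more: the summary moves by a factor of about 4 to 12 (8.4/2.2 to 8.1/0.7) with the patient mix alone.

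This should be corrected before analysis, but its reach is limited. The endpoint is descriptive and secondary, no test depends on it, and the primary analysis, sample size and regressions are untouched.

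**What to change.** Replace the single line in SAP 6.5 by separate variables for each add-on:

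- (a) in patients not on the drug at LCIG initiation, time to first start;
- (b) in patients on the drug at LCIG initiation, time to first dose reduction, with abrupt discontinuation shown separately or explicitly stated as included;
- (c) if wanted, time to first dose increase, reported on its own.

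For each, give the number of patients eligible and the number with the event, and treat patients without an event as censored at the visit. State how use at LCIG initiation is determined for drugs carried over.

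Reconcile the description of the tapering process in SAP 6.5 with the definition in protocol 9.2.7.5; changing the latency line alone would leave the two in conflict.

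The cost is SAP wording and a few more tables. No new data are needed, because the dates and doses are already collected.
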